	
• Navigation to additional psychiatric or substance use services, if needed• Motivational interviewing and brief therapeutic recommendations, if needed
Statistical Analysis	Analyses will include all patients identified as having been discharged and meeting the inclusion criteria. Baseline comparisons of the intervention and usual care groups will be made using univariate analyses. The primary analysis will be conducted using generalized linear mixed models with fixed effects for intervention, and intervention multiply by the time, accounting for the cluster randomized trial design with a random cluster (hospitals) or time (steps) effect. Results will be presented with odds ratios and 95% confidence intervals.

LIST OF ABBREVIATIONS

BHI	Behavioral Health Integration
CORE	Center for Outcomes Research and Evaluation
C-SSRS	Columbia – Suicide Severity Rating Scale
EDW	Enterprise Data Warehouse
VPTC	Virtual Psychiatric Transition of Care
NC	North Carolina
PHI	Private Health Information
PHQ-2	Patient Health Questionnaire - Screener for Depressive Disorders
PHQ-9	Patient Health Questionnaire – Screener for Severity of Depression
SOP	Standard Operating Procedures

TABLE OF CONTENTS

1.1.	Hypothesis.....	8
1.2.	Primary Objective	8
1.3.	Secondary Objectives	8
1.4.	Exploratory Analyses	8
2.	BACKGROUND	9
3.	RATIONALE	9
4.	SUBJECT AND SITE SELECTION	10
4.1.	Accrual.....	10
4.2.	Accrual – Subjects	10
4.3.	Participating sites	10
4.4.	Inclusion\Exclusion Criteria	11
4.4.1.	Inclusion Criteria	11
4.4.2.	Exclusion Criteria	11
4.5.	Evaluable Population	11
5.	OVERALL DESIGN.....	11
5.1.	Variables	11
5.1.1.	Primary Outcome Variable.....	11
5.1.2.	Secondary Outcome Variables	11
5.1.3.	Exploratory Variables	12
5.2.	Trial Design	12
5.2.1.	Justification for stepped wedge cluster randomized control trial	12
5.2.2.	Virtual Psychiatric Transition of Care Program	13
5.2.2.1.	Zero Suicide Pathway	13
5.2.2.2.	VPTC Pathway	13
5.3.	Patient Graduation from the VPTC Program	14
5.4.	Continuation of the Intervention	14
6.	QUALITATIVE REVIEW	14
7.	DATA COLLECTION AND REPORTING.....	15
7.1.	Sample Size Analysis	16
7.2.	Statistical analysis	16
7.3.	Missing Data	17
7.4.	Training	17
7.5.	Data Collection Dates.....	17

8. INTERVENTION PLAN.....	18
8.1. Behavioral Health Professional Assessments.....	18
8.2. Follow-up Assessments.....	18
8.3. Psychiatric Virtual Appointments.....	18
9. STUDY GOVERNANCE	19
10. SAFETY RISKS AND REPORTING.....	19

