5.2. Trial Design

5.2.1. Justification for stepped wedge cluster randomized control trial

The primary aim is to assess the effectiveness of a structured multidisciplinary care plan (intervention), compared with usual care (control) on 30-day all cause non-elective acute care utilization (ED visits, observation, and inpatient encounters). The VPTC program will be delivered at the level of location or cluster, thus minimizing contamination and the risk of selection bias, if subjects were randomized at the individual level. Therefore, the unit of randomization and analysis for this study will be the cluster. Considering logistical constraints and design rigor, the intervention will be rolled out sequentially instead of at the same time. Moreover, substantial and differential cluster-effects may exist because of distinct volume and characteristics of patients in each hospital. Thus, the stepped wedge design is advantageous compared with other alternative designs.

The stepped wedge design implies a baseline period, in which no clusters are exposed to the intervention. Then, at the chosen time interval of three months, one location will be randomized to cross from the control to intervention (Figure 1). This process continues until all seven locations have crossed over to the intervention. The order of this cross over process will be randomized. We will use randomization to assign location order so that if a high or low volume location is assigned cluster 1, a high or low volume location is assigned cluster 7. The single ED location will be assigned to cluster 4. SAS Enterprise Guide version 8.2 will be used for the randomization. Allocation will be communicated only to the behavioral health team initially to prevent contamination. Locations will learn of allocation in the month preceding roll-out. Patients in included locations will be blinded to the intervention or control period.

An example of the roll out schedule

Location	August 2021	November 2021	February 2022	May 2022	August 2022	November 2022	February 2023	May 2023
Location 1	0	1	1	1	1	1	1	1
Location 2	0	0	1	1	1	1	1	1
Location 3	0	0	0	1	1	1	1	1
Location 4	0	0	0	0	1	1	1	1
Location 5	0	0	0	0	0	1	1	1
Location 6	0	0	0	0	0	0	1	1
Location 7	0	0	0	0	0	0	0	1

1=Virtual Psychiatric Transition of Care Program; 0=Usual Care

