7.1. Sample Size Analysis

Calculations of sample size were based on primary analysis of 30-day non-elective acute care utilization on a binary group. Our preliminary data shows that average unique patients in each hospital (cluster size) per three months ranged from 159 to 300, we expected an enrollment rate of 40%. Thus, the average effective cluster size is 96 with a standard deviation of 15. Conservatively, we would at least expect an average cluster size of 81. With the assumption of detecting a change from 20% in the control period to 14% in the intervention period for 30-day non-elective acute care utilization, a mean cluster size of 81 with seven clusters and seven steps (8 time periods inclusive of a control period) would achieve a power of 0.89 if intra-class correlation coefficients (ICC)=0.20 and two-side $\alpha=0.05$. Holding other parameters constant, the larger ICC is, the higher the power we will obtain. The coefficient of variation (CV) of sample size is approximately 0.15. To account for this varying cluster size, we inflated the number of patients by 10% resulting in an average cluster size of 89 patients per three months, resulting in a sample size of 2,495 patients among the intervention group and 4,990 patients overall inclusive of our control population. In this pragmatic trial, those assigned to the intervention but did not enroll in VPTC during the intervention period (around 60%) would also be counted in the intervention arm. It is within our expectation that intervention arm eventually has smaller reduction in 30-day non-elective acute care utilization (i.e. $0.4*0.14 + 0.6*0.20 = 17.6\%$, difference=2.4%). However, we still ensure a power above 0.80 as long as over 2,495 patients actually received VPTC. The power was calculated by using the PASS 15.

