7.2. Statistical analysis

Distributions of baseline characteristics for locations and patients will be compared between the intervention or control periods to assess effectiveness of the randomization, and statistical or clinical differences will be adjusted in sensitivity analyses. All analyses for treatment and control periods comparisons will use an intention-to-treat approach and results will be reported used the CONSORT extension to cluster randomized trials.

The primary outcome for this study is 30-day all cause non-elective acute care utilization. Characteristics of the locations and individuals will be summarized by levels of randomization steps, locations, and individuals. The count, rates and 95% confidence intervals of 30-day non-elective acute

care utilization in the control period will be presented and compared with that in the treatment period. The primary analysis will be conducted using generalized linear mixed models with fixed effects for intervention, and intervention multiply by the time, accounting for the cluster randomized trial design with a random cluster (hospitals) or time (steps) effect. We will estimate and report the intra class correlation coefficients for all outcome measures to assess assumptions for sample size analyses and for future investigations using similar designs and outcomes. The primary analyses will follow the intention to treat principle with an additional per protocol analysis including those who actually used VPTC. The secondary analyses will include within cluster comparisons of intervention and control periods (not adjusting for any confounding effect of time), as well as comparisons of a series of (unbalanced) quasi-parallel cluster trials between those enrolled and unenrolled clusters at each intervention enrollment period. The same analyses plan will also be applied to secondary outcomes.

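### The rule that a larger ICC gives more power fails below an ICC of about 0.03 and reverses if location rates vary by quarter; the primary model names no location-by-period effect to keep its interval valid in that case

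*Combined protocol and SAP*

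**What the plan says.** Section 7.1 bases the sample size on a fall from 20% to 14% in 30-day utilization, with seven locations, eight three-month periods, 81 patients per location-period, an ICC of 0.20 and two-sided alpha of 0.05. It reports power of 0.89 and then states: "Holding other parameters constant, the larger ICC is, the higher the power we will obtain". It gives no other ICC and says nothing about how the correlation behaves between quarters.

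Section 7.2, repeated in the synopsis, specifies a generalized linear mixed model with fixed effects for intervention and intervention-by-time, "accounting for the cluster randomized trial design with a random cluster (hospitals) or time (steps) effect". It lists no location-by-period effect, no fixed period effect and no small-sample reference distribution. The synopsis adds: "Results will be presented with odds ratios and 95% confidence intervals". Section 7.2 also promises a check: "We will estimate and report the intra class correlation coefficients for all outcome measures to assess assumptions for sample size analyses".

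**The concern.** The ICC sentence reads as reassurance that an ICC above plan can only help. In a stepped wedge that depends on each location's underlying rate staying constant over time, so that a location serves as its own control across quarters. With one location crossing every three months over about two years, that is a strong assumption, and the sentence does not state it.

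The same assumption sits in the primary model. A random location effect absorbs stable differences between locations. A step effect absorbs changes that all locations share. An intervention-by-time term describes the treatment effect. None of them absorbs a quarter in which one location's rate moves by itself. If such variation exists, it is left out of the standard error: the 95% interval is too narrow and the test rejects too often. The promised ICC report would not reveal this, because a single location effect yields a single ICC and cannot show whether it holds from one quarter to the next.

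**Working it through.** **Inputs.** From Section 7.1: rates 20% and 14%, I = 7 locations, T = 8 periods, m = 81, ICC 0.20, alpha 0.05 two-sided. From the roll-out table in Section 5.2.1: one location crosses per step. Total variance is 0.20 × 0.80 = 0.16. CAC, the share of the between-location variance that persists across quarters, is not in the documents. It is assumed, over 0.8 to 1.

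**Formula.** Let τ = 0.16 × ICC × CAC, γ = 0.16 × ICC × (1 − CAC) and s = 0.16 × (1 − ICC)/m + γ. With fixed periods,

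Var = I·s·(s + T·τ) / [(I·U − W)·s + (U² + I·T·U − T·W − I·V)·τ],

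where U = 28 exposed location-periods, W = 140 (squared numbers of exposed locations, summed over periods) and V = 140 (squared numbers of exposed periods, summed over locations). The brackets are 196 − 140 = 56 and 784 + 1568 − 1120 − 980 = 252. Power = Φ(0.06/SE − 1.96).

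**The plan's figure (ICC 0.20, CAC 1).** τ = 0.032 and s = 0.128/81 = 0.00158. Var = 7 × 0.00158 × 0.2576 / (0.0885 + 8.064) = 0.000350, so SE = 0.0187. Power = Φ(3.21 − 1.96) = 0.894. The stated 0.89 is reproduced.

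**Other ICCs, CAC 1.**
- ICC 0: Var = s/8, SE 0.0157, power 0.968.
- ICC 0.01: SE 0.0198, power 0.856.
- ICC 0.032: SE 0.0203, power 0.842 (the minimum).
- ICC 0.10: SE 0.0198, power 0.859.

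**With location-by-quarter variation (same formula).**

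| CAC | ICC 0.01 | ICC 0.05 | ICC 0.20 |
|---|---|---|---|
| 1 | 0.856 | 0.844 | 0.894 |
| 0.99 | 0.854 | 0.829 | 0.834 |
| 0.95 | 0.845 | 0.772 | 0.621 |
| 0.9 | 0.834 | 0.706 | 0.458 |
| 0.8 | 0.813 | 0.599 | 0.304 |

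At ICC 0.20 the slope of power on ICC changes sign at CAC 0.988, which is a location-by-quarter SD of √(0.16 × 0.20 × 0.012) = 2.0 points. The lowest entries are extreme: ICC 0.20 with CAC 0.9 means an SD of 5.7 points. ICC 0.05 with CAC 0.9 means 2.8 points, and ICC 0.01 with CAC 0.9 means 1.3 points.

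**The interval.** At ICC 0.05 and CAC 0.9, γ = 0.0008. With 81 per location-period, a random-intercept model uses 0.152/81 = 0.00188 where the true value is 0.00268. The SE is then too small by a factor of about √(0.00268/0.00188) = 1.19, and type I error is 2Φ(−1.96/1.19) = 10%.

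The intention-to-treat analysis includes all eligible discharges, and Section 7.1 says "average unique patients in each hospital (cluster size) per three months ranged from 159 to 300". So 222 per location-period (89/0.4) is a reasonable assumed size. The factor there is 1.47 and type I error 18%.

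**Logistic simulation.** Mean rate 20%, fixed periods, location random intercept only, normal reference, 10,000 trials per scenario (5,000 for the last two rows). Type I error:

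| Patients per location-period | ICC | CAC 1 | CAC 0.9 | CAC 0.8 |
|---|---|---|---|---|
| 81 | 0.01 | 5.8% | 6.5% | 7.9% |
| 81 | 0.05 | 5.7% | 9.9% | 14.7% |
| 222 | 0.01 | 5.7% | 8.0% | 10.8% |
| 222 | 0.05 | 5.0% | 16.8% | 28.0% |
| 159 to 300, evenly spread | 0.01 | 5.7% | 7.8% | 11.8% |
| 159 to 300, evenly spread | 0.05 | 5.5% | 18.8% | 29.7% |

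At CAC 1, simulated power of this model for the 6-point difference at 81 per location-period is 0.895 / 0.876 / 0.880 at ICC 0.01 / 0.05 / 0.20 (3,000 trials).

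**The case against.** The sentence carries its own condition and directly follows a calculation at ICC 0.20, where it is true. In the logistic model, which is nearer to what Section 7.2 plans, power is nearly flat at about 0.88 to 0.90 from ICC 0.01 upward, so the dip to 0.842 belongs to the linear approximation. Even 0.842 exceeds the 0.80 named in Section 7.1. All of this stands. With stable rates the sentence is a minor wording fault, although flat power does not bear out the stated rule either.

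It also stands that the harm depends on an assumed CAC, and that the simulated model is not exactly the plan's: it omits the intervention-by-time term and includes fixed periods that Section 7.2 does not name.

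Four stronger readings are tempting, and the documents do not support them.
- **That 0.89 is wrong.** It reproduces.
- **That the location effect might be dropped because of the word or.** Section 5.2.1 says "the unit of randomization and analysis for this study will be the cluster", and Section 7.2 sets its primary model against secondary "within cluster comparisons of intervention and control periods (not adjusting for any confounding effect of time"). A location effect and a time adjustment both appear intended.
- **That power never rises with ICC if the within-location variance is held at 0.16.** At ICC 0.20 that needs a total variance of 0.16/0.8 = 0.20, which a binary outcome with a 20% rate cannot have.
- **That the primary test is shown to be anti-conservative.** At CAC 1 it is close to 5%.

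**Conclusion.** The point holds in two parts. First, the ICC sentence is not a general rule. In the calculation behind 0.89 it is true only above an ICC of about 0.03, and at the planned 0.20 it reverses below an assumed CAC of about 0.988. Second, the primary model as written has no term for location-by-quarter variation beyond the shared time trend. If that variation exists, the interval is too narrow and power for the 6-point difference is below 0.89. The likely size cannot be read from the documents. Over the assumed range it runs from negligible (CAC 1) to type I error of two to three times nominal or more (ICC 0.05, CAC 0.9, with the patient numbers of an intention-to-treat analysis). It should be corrected because the protection is cheap and the planned output could not reveal the problem.

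Power for the diluted 2.4-point difference is a separate matter. Section 7.1 acknowledges the dilution ("It is within our expectation that intervention arm eventually has smaller reduction in 30-day non-elective acute care utilization"), and none of the 6-point figures above apply to it.

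**What to change.** 1. In Section 7.1, delete the ICC sentence. Put in its place a power table over ICC 0.01 to 0.20 and CAC 0.8 to 1, computed for the revised primary model and reference distribution. For the 6-point difference at 81 per location-period and CAC 1, simulated power is then 0.865 / 0.843 / 0.851 at ICC 0.01 / 0.05 / 0.20, that is, about 0.84 to 0.87 rather than 0.89. State that the table does not apply to the 2.4-point intention-to-treat difference.
2. In Section 7.2 and the synopsis, replace the random-effects clause with: fixed effects for period (step), and random effects for location and for location-by-period. Report the within-period and the between-period ICC.
3. Name the estimation method and reference distribution: restricted pseudo-likelihood with t on about 41 degrees of freedom (56 location-periods − 7 locations − 7 period contrasts − 1 intervention effect; 40 if intervention-by-time is kept as one linear term), or another small-sample correction shown to hold 5%. Restricted estimation matters: the same model fitted by maximum likelihood with t(41) gave 6.8% to 8.2% at ICC 0.05 and CAC 0.9 and 0.8.

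With these changes, simulated type I error is 3.6% to 5.8% over the 18 scenarios tabulated above.

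**Cost.** Wording, one table and one extra variance component. If rates are stable, the test is slightly conservative (3.6% to 4.8%) and power falls by about 0.03. If they vary, intervals widen to their correct length: at CAC 0.9 and 81 per location-period, simulated power for the 6-point difference is 0.76 at ICC 0.05 and 0.53 at ICC 0.20.

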4. SUBJECT AND SITE SELECTION

4.1. Accrual

For this study, all patients discharged that meet the inclusion criteria are eligible for analyses. Patients meeting eligibility criteria will accrue in both the intervention and usual care arms of the study.

A weekly list will be generated indicating patients discharged the prior week at any of the participating locations. The list contains inpatient and observation encounters. The list will identify discharged patients at facilities throughout the project, not just once the facility has implemented the VPTC program. For the purposes of this project, we are not enrolling towards a targeted patient accrual. We will enroll patients during a pre-determined data collection period, See Section 5.

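### Section 7.1's total of 4,990 applies the 40% program enrollment rate to control quarters and is not the size of any analysis the plan describes; the intention-to-treat set is about 11,300 to 13,400

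*Combined protocol and SAP*

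**What the plan says.** Section 7.1 (Sample Size Analysis) starts from quarterly hospital volume: "average unique patients in each hospital (cluster size) per three months ranged from 159 to 300". It then applies an uptake figure, "we expected an enrollment rate of 40" per cent, and concludes that "the average effective cluster size is 96 with a standard deviation of 15". It steps down once more: "Conservatively, we would at least expect an average cluster size of 81". Power of 0.89 is quoted at that size, with an ICC of 0.20 and two-sided alpha of 0.05, for "detecting a change from 20% in the control period to 14% in the intervention period". The size is then raised by 10% for unequal clusters, "resulting in a sample size of 2,495 patients among the intervention group and 4,990 patients overall inclusive of our control population".

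The same section goes on to say that the roughly 60% of intervention-period patients who do not enroll also count in the intervention arm. It expects their inclusion to shrink the difference to 2.4 points (20% versus 17.6%). It claims power above 0.80 provided that more than 2,495 patients actually receive VPTC.

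On who is analyzed, Section 4.1 says that "all patients discharged that meet the inclusion criteria are eligible for analyses" and that weekly discharge lists cover facilities before as well as after go-live. Section 4.5 assesses all eligible patients in both groups for the primary outcome by intention to treat, and Section 7.2 repeats that principle. Section 4.2 defines usual-care patients as those seen at locations not using VPTC. On targets, Section 4.1 says that "we are not enrolling towards a targeted patient accrual".

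**The concern.** The 40% is uptake of VPTC, so it has meaning only in a quarter when a location offers VPTC. Section 7.1 nevertheless carries it into every location-quarter, and so counts 40% of the control patients when the plan analyzes all of them. On the intervention side, 2,495 is labelled as the intervention group, while the next lines of the section treat it as the number who receive VPTC and place the non-enrollers in that arm too.

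Section 7.1 gives no other overall size. A reader who sets the final CONSORT report beside the plan would find more than twice the planned number of patients, with nothing to explain the difference. The label also blurs two quantities that the power argument must keep apart: the number analyzed and the number treated.

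**Working it through.** **Inputs.** From Section 7.1: volume 159 to 300 per hospital per quarter; enrollment 40%; effective cluster size 96 (SD 15); conservative size 81; inflation 10%; 7 clusters, 8 periods; ICC 0.20; 20% versus 14%, diluted to 17.6%. From the example roll-out table in Section 5.2.1: 7 x 8 = 56 location-quarters, of which 7 + 6 + 5 + 4 + 3 + 2 + 1 = 28 are intervention and 28 are control.

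**Reproducing the plan's totals**
- 81 = 96 - 15, and 81 x 1.1 = 89.1
- 28 x 89.1 = 2,494.8, rounded to 2,495
- 56 x 89.1 = 4,989.6, rounded to 4,990

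Both match, so the multiplication is right. The fault lies in the population counted: 28 of the 56 cells are control cells, and each has been cut to 40%.

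**Size of the intention-to-treat set.** The expected volume implied by the plan is 96 / 0.4 = 240 per location-quarter.
- Expected volume: 240 x 56 = 13,440, or 6,720 per condition
- If 81 reflects lower volume at 40% uptake: 81 / 0.4 = 202.5, and 202.5 x 56 = 11,340, or 5,670 per condition
- If 81 reflects lower uptake at unchanged volume: 81 / 240 = 33.75% uptake, and the total stays at 13,440
- Outer bounds, one volume in every cell: 159 x 56 = 8,904 and 300 x 56 = 16,800

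Even the lowest of these is well above 4,990.

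**Expected VPTC recipients (28 intervention cells)**
- At 81: 28 x 81 = 2,268, which is 2,495 - 2,268 = 227 short of the plan's condition
- At 96: 28 x 96 = 2,688, which is 193 above it

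The 10% inflation supplies no patients. Locations and quarters are fixed and there is no accrual target, so multiplying 81 by 1.1 changes only the number on the page.

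**What the 0.89 power belongs to.** The Hussey-Hughes stepped-wedge variance is

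Var = I s (s + T t) / [(IU - W) s + (U² + ITU - TW - IV) t]

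Here s is the within-cluster variance divided by the cell size and t is the between-cluster variance. For this design I = 7, T = 8, U = 28, W = 140 and V = 140, so IU - W = 56 and the last bracket is 784 + 1,568 - 1,120 - 980 = 252.
- Total variance 0.20 x 0.80 = 0.16; with ICC 0.20, t = 0.032 and s = 0.128 / 81 = 0.00158
- Var = 0.0003495, SE = 0.0187
- Power = Φ(0.06 / 0.0187 - 1.96) = 0.894, against the stated 0.89

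So 0.89 is the power at 81 per cell for a 6-point difference. Under the same convention, the plan's diluted difference of 2.4 points gives:
- 202.5 per cell, ICC 0.01: SE 0.0129, power 0.46
- 240 per cell, ICC 0.20: SE 0.0109, power 0.60

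The ICC range of 0.01 to 0.20 is an assumption; the plan gives only 0.20.

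**The case against.** The best defense is that 4,990 is a required minimum and not a forecast. Section 7.1 starts from a size that gives 0.89 power and inflates it for unequal clusters, which is how a required size is usually built. It also tells the reader that non-enrollers join the intervention arm, so that arm must exceed 2,495. Part of this stands: the intervention side is partly disclosed, and no recruitment decision depends on the number. But the section nowhere calls 4,990 a minimum, presents it as including the control population, and never restates the control side, where a 40% subset has no meaning.

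Several stronger readings are tempting, and the documents do not support them.
- A reader might infer that the plan presents 2,495 recipients as secured. It does not; it makes that number a condition, which its expected cluster size meets.
- A reader might infer that monitoring or stopping runs off 4,990. Nothing ties either to it. Section 4.1 disclaims a target, Section 7 reports eligible and enrolled counts separately, and Section 10.3 sets no numeric threshold.
- A reader might divide 89.1 by 0.4, multiply by 56 and give a single corrected total of 12,474. That keeps the 10% that adds no patients, so a range is the honest statement.
- A reader might say that a control group of 2,495 is ruled out in the per-protocol analysis. Section 7.2 does not define that comparator, so such a group is undescribed but not excluded.

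**Conclusion.** The point holds. The totals in Section 7.1 are correctly multiplied but count the wrong population, and 4,990 is not the size of the primary analysis or of any analysis the plan describes. The intention-to-treat set is about 11,300 to 13,400, which is 2.3 to 2.7 times the stated total (11,340 / 4,990 and 13,440 / 4,990). Recipients are expected to number about 2,270 to 2,690, a range that straddles the plan's 2,495.

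These figures rest on three assumptions. The volume of 240 is implied by 96 / 0.4 and is not stated. The 159 to 300 are taken as eligible patients, although the section does not say that they were screened for residency or a telephone number. The input is unique patients per quarter, so a patient seen in two quarters counts twice in the total, and distinct people may be fewer.

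A reader might also infer that a larger analysis set means a better-powered trial. The check above does not support that: with the diluted difference, power is about 0.46 to 0.60 under the stated convention and assumed ICC range. Whether the claim of power above 0.80 can stand is a separate question. Here it means only that the corrected totals must not be placed beside the 0.89 as if they supported it.

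**What to change.** In Section 7.1:
1. Replace 2,495 and 4,990 with the expected number of eligible patients, about 5,700 to 6,700 per condition and about 11,300 to 13,400 overall, and say that these count unique patients per location-quarter.
2. State separately that about 2,270 to 2,690 patients in intervention quarters are expected to receive VPTC, and that the condition of more than 2,495 recipients is met at 96 per location-quarter but not at 81.
3. Say that the 10% allowance for unequal clusters does not add patients to the trial.
4. Say that the 0.89 power was computed at 81 per location-quarter for 20% versus 14%, and that it does not carry over to the intention-to-treat set with its 2.4-point difference.

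The cost is a few sentences in one section. Sites, schedule, data collection and conduct do not change.

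### Section 7.1 promises power above 0.80 for the diluted intention-to-treat contrast (20% vs 17.6%), but the plan's own inputs give about 0.57, and roughly 0.4 to 0.6 depending on the model

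*Combined protocol and SAP*

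**What the plan says.** Section 7.1 starts from site volumes: "average unique patients in each hospital (cluster size) per three months ranged from 159 to 300". With 40% enrollment, "the average effective cluster size is 96 with a standard deviation of 15", and the calculation uses a conservative 81. For 20% vs 14%, seven clusters, eight periods, ICC 0.20 and two-sided alpha 0.05, it reports power of 0.89 from PASS 15. Cell size is then raised by 10% to 89, "resulting in a sample size of 2,495 patients among the intervention group and 4,990 patients overall".

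The same paragraph says that intervention-period patients who do not enroll (around 60%) "would also be counted in the intervention arm". From this it derives an expected rate of 0.4 × 14% + 0.6 × 20% = 17.6%, a difference of 2.4 points. The next sentence reads: "However, we still ensure a power above 0.80 as long as over 2,495 patients actually received VPTC".

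Section 7.2 fixes the analysis set: "The primary analyses will follow the intention to treat principle with an additional per protocol analysis including those who actually used VPTC". Section 4.5 likewise assesses the primary outcome in all eligible patients by intention to treat.

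**The concern.** The 0.89 belongs to an effect of 6 points. The primary analysis is expected to see 2.4 points, and no calculation is shown for that contrast.

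Including the non-enrollees multiplies the sample by 2.5 (1/0.4) and the effect by 0.4. Precision improves roughly with the square root of the sample, so the test signal becomes about 0.4 × √2.5 = 0.63 of its size in the 89-patient, 6-point case. A loss of that size cannot leave power above 0.80 when the starting point is about 0.9.

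At stake is how a non-significant result is read. Readers are told that the chance of missing the expected effect is under 20%, when it is nearer one half. Nothing else in the plan would catch this. Section 4.1 sets no accrual target. The reports in Section 7 and the meetings in Section 10.3 would show uptake and enrollment, but they carry no rule linked to power.

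**Working it through.** **Inputs.** From Section 7.1: I = 7 clusters, T = 8 periods, ICC 0.20, two-sided alpha 0.05, rates of 20%, 14% and 17.6%, 40% uptake, and m = 81 and 89.1 (81 × 1.1) per site-quarter. From the roll-out table in Section 5.2.1: one site crosses per step, giving 28 control and 28 intervention cells. The PASS procedure and variance settings are not stated, so the method below is inferred from its match to 0.89.

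**Sample implied by the claim.** 89.1 × 28 = 2,495 and 89.1 × 56 = 4,990, which match the plan. If 2,495 received the program at 40% uptake, eligible patients per cell are 89.1/0.4 = 222.75, and the total is 222.75 × 56 = 12,474. The plan's expected volume is 96/0.4 = 240 per cell.

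**Formula.** Hussey-Hughes variance with a random cluster intercept and fixed period effects:

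Var = I·s²·(s² + T·τ²) / [(I·U − W)·s² + (U² + I·T·U − T·W − I·V)·τ²]

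- Total variance is 0.20 × 0.80 = 0.16, so τ² = 0.20 × 0.16 = 0.032 and s² = 0.80 × 0.16/m = 0.128/m.
- U (number of intervention cells) = 28; W (sum of squared period totals) = 140; V (sum of squared site totals) = 140.
- I·U − W = 196 − 140 = 56.
- U² + I·T·U − T·W − I·V = 784 + 1,568 − 1,120 − 980 = 252.
- Power = Φ(difference/SE − 1.96).

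**Stated case** (m = 81, 6 points). s² = 0.00158. Var = 7 × 0.00158 × 0.2576 / (0.088 + 8.064) = 0.000350, so SE = 0.0187. Power = Φ(3.21 − 1.96) = 0.894, which reproduces the plan's 0.89.

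**Primary contrast** (m = 222.75, 2.4 points). s² = 0.000575. Var = 7 × 0.000575 × 0.2566 / (0.032 + 8.064) = 0.000127, so SE = 0.0113. Power = Φ(2.13 − 1.96) = 0.566.

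| Eligible per site-quarter, 20% vs 17.6%, ICC 0.20 | Power |
|---|---|
| 89.1 (only 4,990 patients analysed) | 0.27 |
| 222.75 (2,495 recipients at 40%) | 0.57 |
| 240 (plan's expected mean) | 0.60 |
| 300 (every site at the stated maximum) | 0.69 |

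**What 0.80 would need at ICC 0.20.** About 387 eligible per site-quarter, or 387 × 28 × 0.4 ≈ 4,330 recipients. The stated maximum volume yields 300 × 28 × 0.4 = 3,360. Alternatively, at 222.75 per cell the detectable difference is (1.96 + 0.84) × 0.0113 ≈ 3.16 points. If recipients keep a 6-point effect, that requires uptake of 3.16/6 ≈ 53%.

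**Sensitivity at about 223 per cell.**
- *Variance convention* (ICC 0.20): 0.48 to 0.59.
- *Logistic models with period effects* (ICC 0.20, simulated; beta-distributed cluster risks are my assumption): 0.55–0.57 with the odds ratio set so that average risk is 17.6%; 0.51–0.52 with a constant risk ratio of 0.88; 0.39–0.42 with a constant odds ratio of 0.854, which delivers only about 2.0 points on average.
- *Other ICCs* (my assumption; the plan gives only 0.20): 0.72 at ICC 0 and 0.49–0.50 at 0.01–0.05. No ICC from 0 to 0.20 reaches 0.80; it takes about 0.54.

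**Two smaller points in the same paragraph.** The total of 4,990 applies the 40% enrollment rate to control periods, where nobody can enroll, so it is not the intention-to-treat sample. The statement that power rises with the ICC is not general: for 81 per cell and 6 points, power falls from 0.968 at ICC 0 to a minimum of 0.842 near ICC 0.03, then rises to 0.894 at 0.20.

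**The case against.** **A model without period effects does exceed 0.80.** It gives 0.90 for the diluted contrast at 223, and Section 7.2 lists no main effect of time. But the same model gives 0.998 for the stated case, so it is not the source of 0.89. Section 7.2 also describes certain secondary comparisons as "not adjusting for any confounding effect of time", which implies that the primary analysis does adjust. That is an inference; the plan does not say so outright.

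**Period could be a random effect**, since the model is described as "accounting for the cluster randomized trial design with a random cluster (hospitals) or time (steps) effect". Power then reaches 0.80 only if the between-period SD is about 0.8 percentage points or less, and the stated case would be 0.995, not 0.89.

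**The model as written includes an intervention-by-time term.** Power for the intervention coefficient then depends on where time is centred. A linear approximation at 223 and ICC 0.20 gives 0.17 to 0.57 with period effects and 0.28 to 0.89 without. This stands: 0.4 to 0.6 does not bound every reading of Section 7.2. It does not rescue the claim, because the versions that reach 0.80 give about 0.99 for the stated case.

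**The lower end of the range is for a smaller effect.** This is true of the constant-odds-ratio figures. For an average difference of 2.4 points at 223 and ICC 0.20, the normal-approximation and logistic results above run from 0.48 to 0.59. Small-sample t tests in the linear calculation give about 0.41 to 0.55.

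**The sentence may mean recipients only.** For 20% vs 14% with 89.1 per cell, power is 0.92, and a per-protocol analysis is planned. But the sentence directly follows the 2.4-point difference and opens with a contrast to it. On the recipients-only reading, no power is stated for the primary contrast, so Section 7.1 still needs correcting.

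**The harm is to interpretation, not to bias.** This is correct, but the figure concerns the primary analysis and determines how a null result is read.

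**Conclusion.** The claim is wrong as written and must be corrected. No version tried gives both 0.89 for the stated case and more than 0.80 for 20% vs 17.6%. The calculation that reproduces 0.89 gives 0.57 at the plan's own threshold of 2,495 recipients, and even maximum volume at every site gives only 0.69.

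This rests on three assumptions: the inferred PASS settings, adjustment for period in the primary model, and constant within-site correlation over time. The last is favourable to the plan: an assumed cluster autocorrelation of 0.95 would bring power down to about 0.2.

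**What to change.** 1. Delete the sentence claiming power above 0.80.
2. In Section 7.2, name the period term and the random effects of the primary model. Do this first, so that the two sections agree.
3. Recompute power for that model. State the PASS procedure and variance settings, and show an ICC range that includes values near zero.
4. Replace the deleted sentence with text along these lines, updated to the final model:

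> The primary intention-to-treat analysis includes all eligible discharges in both periods: about 223 per site-quarter (12,474 in total) if 2,495 patients receive VPTC at 40% uptake. For 20% vs 17.6%, power is about 0.57 at ICC 0.20 and about 0.50 at ICC 0.01–0.05 (Hussey-Hughes, 7 clusters, 8 periods, fixed period effects, total variance p0(1 − p0), two-sided 0.05). It ranges from about 0.4 to 0.6 with the model and the scale of the effect. By the same calculation, 80% power is available for a difference of about 3.2 points at ICC 0.20 and 3.5 points at ICC 0.01–0.02.

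5. Give the sample size as all eligible discharges instead of 4,990. Limit the ICC sentence to values above about 0.03, naming the case it applies to (81 per site-quarter, 20% vs 14%).

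The cost is one recalculation and a rewritten paragraph, plus a clarification in Section 7.2. No patients are added and the design does not change. The downside is a less favourable stated power for the primary analysis.
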